Multiple substance use among young adults. [name] has led studies examining multiple substance use among young adults, including reports of a project evaluating patterns of tobacco and marijuana use among young adults (N=1987) surveyed online. We showed that marijuana use was more prevalent than previously reported among young adult smokers,¹¹³ that co-users of tobacco and marijuana used tobacco more heavily and had a lower likelihood of wanting to quit tobacco compared to marijuana,¹¹⁴ and that co-users showed marked differences in motivation and thoughts about abstinence toward marijuana compared to

tobacco.¹¹⁵ Studies of multiple health risk behaviors among our group have shown that alcohol use is common among young adult smokers¹¹⁶ and smokers in mental health treatment.¹¹⁷

Analyses of Social Media Data. [name] group has used social network analysis to examine patterns of substance use interactions on social media.^{109, 118-121} In an analysis of the TSP feasibility trial data, Ping, [name], and [name] found that a monetary incentive was associated with "any" engagement (commenting on Facebook posts) in TSP for those not ready to quit, while an incentive was associated with extent of engagement among those commenting at least once in all readiness to quit groups.¹⁰⁹ Another study using Facebook data, Zhang and [name] analyzed the content of posts and comments in an online forum for smoking cessation (Quitnet).¹²² They identified dominant patterns of social support including "initiated support" that was offered voluntarily and "invited support" that was offered in response to requests and most prevalent. In an effort to tie patterns of social interactions to smoking cessation outcomes, Zhang and [name] examined features of posts and users that were related to engagement on QuitNet.¹²³ Posts that received the most and the fastest comments from Facebook users tended to ask for responses of user motivations, methods, experiences and emotions of smoking abstinence. Users in the maintenance stage of smoking cessation were more active (made comments more frequently and immediately) than those at the early action stage of readiness to quit smoking. Personal communications and advice were the most popular types of informational support. **This work forms the basis for incorporating an incentive into our intervention, and informs analytic strategies with Facebook data to accomplish Specific Aim 3.**

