Sample size and power analysis. The sample N of 160 was set primarily for practical and clinical reasons and not driven by estimated effect sizes or hypothesis testing. We expect to have representation (although not equal) among males and females, and across ethnic groups consistent with our current trial of TSP. We also expect to have representation across levels of smoking and drinking, and readiness to quit using both substances. We anticipate an attrition rate of 30% at 3, 6, and 12 months, yielding a final sample size of 112 (56 in each group), enabling us to compare groups on primary and secondary outcomes at each timepoint. This will also generate an effect size estimate that will be useful for powering a larger trial.

A goal of 6 participants will be recruited per week during the 6-month recruitment period, which is in line with recruitment for our feasibility trial and current RCT.¹¹¹

Procedures. Participants will be recruited through Facebook and Craigslist advertisements, using a similar strategy to that of focus group and usability-testing. All advertisements will provide a link to the study’s website, with eligibility questions. If respondents are eligible, then they will be taken to the informed consent webpage. Participants consenting to participate in the study will be asked to verify age by sending proof through email or social media, a process used successfully in [name] previous research. Verified participants will be emailed a baseline assessment. Those completing the baseline assessment will be randomized to either TSP, or TSP+ALC, stratified based on readiness to quit smoking (Ready in the next 30 days, Not Ready in 30 days) and smoking pattern (daily vs. non-daily), variables known to be related to outcomes and addressed by the intervention.¹⁶¹ A stratified random assignment program will be developed in consultation with [name], and used currently in [name] RCT of TSP. All participants will then be assigned to a secret group tailored to their condition and readiness to quit tobacco. Groups will begin when there are approximately 12 participants enrolled, as that has been deemed the optimal number based on analyses of engagement in our previous work.^{109, 162} Groups will receive one social media post daily for 90 days and weekly “The [name] In” counseling sessions managed

[figure not shown]

Figure 2. Participant flow through the study

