Analyses for Specific Aim 3 (Engagement and Patterns of Social Interaction). Analyses will use Facebook data extracted from the private groups we develop on Facebook using the Facebook API. All data will be de-identified and transferred to **[name]**, expert on social media analytics at Drexel University, for analysis. The data will include the content of the posts and comments, the activity of each participant (e.g., number, content, and time of all comments), and interactions among participants. We will determine patterns of engagement, type of posts that are most “engaging” to participants, and relate engagement to smoking and drinking outcomes using three main analyses: **(1) Patterns of engagement:** Total number of “likes” and comments to Facebook groups over the 3 month intervention period will be tallied for each group (TSP, TSP+ALC), and the non-parametric Kruskal-Wallis ANOVA will compare likes and comments in each intervention and include covariates of baseline characteristics (readiness to quit tobacco/alcohol, daily/non-daily smoking status, gender) and group membership; a social network analysis will examine the interaction patterns among different types of users with which participants engage in each intervention; a content analysis will evaluate the content of comments within each group and observe differences among the two groups; **(2) Success of specific posts:** To evaluate which posts are most successful at engaging participants, Drs. [name] and [name] will collaborate on coding posts based on content type (e.g., alcohol/tobacco, Motivational Interviewing, specific CBT skills). Specific codes will be determined upon design of the TSP+ALC intervention). ANOVA will then be used to examine likes and comments by post type within each group (TSP, TSP+ALC) **(3) Engagement and outcomes:** We will compare TSP and TSP+ALC groups on the relationship between intervention engagement (FB comments) and primary tobacco and alcohol outcomes (abstinence, heavy drinking days) at the end of the 3 month intervention period. Logistic regression will be used to analyze tobacco abstinence, and linear regression for days of heavy drinking at 3 months, controlling for any baseline differences in treatment groups. Kruskal-Wallis tests will evaluate the effect of incentive condition (personal, altruistic, no incentive) on comments to the Facebook group, in both the full sample and only those who made at least one comment to the group to address likely skewed data.

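### The Aim 3 engagement-outcome models choose covariates by arm imbalance, so readiness to quit can confound the within-arm associations

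*Combined protocol and SAP*

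**What the plan says.** C.9, Specific Aim 3, item (3) sets the target: "We will compare TSP and TSP+ALC groups on the relationship between intervention engagement (FB comments) and primary tobacco and alcohol outcomes", at the end of the 3-month intervention. Abstinence is modelled by logistic regression and heavy drinking days by linear regression, in both cases "controlling for any baseline differences in treatment groups". No covariate is named.

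Item (1) of the same aim, which compares likes and comments between the interventions, does name covariates: "readiness to quit tobacco/alcohol, daily/non-daily smoking status, gender", together with group membership.

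C.8, Procedures, says that randomisation is "stratified based on readiness to quit smoking (Ready in the next 30 days, Not Ready in 30 days") and on daily versus non-daily smoking, and describes these as "variables known to be related to outcomes and addressed by the intervention". It adds: "All participants will then be assigned to a secret group tailored to their condition and readiness to quit tobacco".

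Wider covariate rules do appear in C.9. The primary model takes variables related to abstinence, and the secondary models take covariates from the smoking literature. Both rules sit under Specific Aim 2. Nothing extends them to Aim 3, and nothing says that the stratification factors enter every model.

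**The concern.** Treatment arm is randomised; commenting is not. Adjusting for variables that happen to differ between arms protects the arm comparison. It does not protect an association between a self-chosen behaviour and an outcome. For that association the relevant variables are those linked to both commenting and outcome, and a variable can be perfectly balanced between arms and still confound it.

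Readiness is the obvious candidate. The plan calls it related to outcome (C.8), lists it as a covariate for engagement (item (1)), and uses it to decide which Facebook group a participant joins. It is then absent from the one model that links engagement to outcome. Because it is a stratification factor, a rule triggered by arm imbalance is also unlikely to bring it in.

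If participants who are ready to quit both comment more and quit more, commenting will look helpful within an arm even when it has no effect. Aim 3 is meant to relate engagement to outcomes and to inform later digital interventions, so the slope within each arm will be read as well as the contrast between arms.

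**Working it through.** **Step 1. The plan's own figure.** C.8 gives N = 160 and 30% attrition: 160 × (1 − 0.30) = 112, or 56 per arm. This reproduces.

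**Step 2. Would the stated rule select readiness?** Trials of 160 were simulated with assignment stratified on readiness and daily smoking. From the documents: 88% daily smokers (current trial, C.5), and either 19% ready (current trial, preliminary-work section) or 50% ready (C.5 plans 4 Ready and 4 Not Ready groups per condition). Assumed: permuted blocks of 4, and p < 0.05 as the definition of a baseline difference, since the plan gives neither. Readiness was flagged in 0 of 4,000 trials at each prevalence, against about 5% under simple randomisation.

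**Step 3. Bias when there is no true engagement effect.** Model: logit P(abstinent) = a + b × arm + c × engagement, with or without readiness. Engagement is standard normal plus d × readiness, then rescaled to SD 1, and arms are balanced on readiness. Assumed: abstinence 15% if not ready and 30% or 45% if ready; d from 0.3 to 1.0 SD. Odds ratios come from 400,000 simulated people, and false-positive rates (two-sided 5%) from 1,500 trials of 112.

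| Ready | Abstinence, not ready / ready | d | OR per SD, unadjusted | OR per SD, adjusted | False positives, unadjusted | False positives, adjusted |
|---|---|---|---|---|---|---|
| 19% | 15% / 30% | 0.3 | 1.05 | 1.00 | 5.1% | 4.7% |
| 19% | 15% / 30% | 1.0 | 1.16 | 1.00 | 7.9% | 4.7% |
| 19% | 15% / 45% | 0.3 | 1.08 | 1.00 | 6.4% | 4.5% |
| 19% | 15% / 45% | 1.0 | 1.31 | 1.01 | 19.9% | 4.7% |
| 50% | 15% / 30% | 0.3 | 1.06 | 0.99 | 5.2% | 5.6% |
| 50% | 15% / 30% | 1.0 | 1.22 | 1.01 | 13.5% | 5.9% |
| 50% | 15% / 45% | 0.3 | 1.12 | 1.00 | 8.5% | 5.1% |
| 50% | 15% / 45% | 1.0 | 1.38 | 1.00 | 33.5% | 5.4% |

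Where readiness was unrelated to engagement (d = 0) or to abstinence (15% in both groups), the unadjusted odds ratio was 0.99 to 1.01. Both links are needed for bias.

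**Step 4. The between-arm comparison.** In the same simulations the arm-by-engagement interaction odds ratio was 0.98 to 1.01, because the confounding was equal in the two arms.

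**Step 5. A second model, at low abstinence.** Overall abstinence 7.1% (verified, completed cases, TSP arm of the current trial) and 19% ready. Assumed: ready participants quit 2 times as often and comment 1.5 times as much, or 4 and 2 times. Comments are gamma-Poisson with mean 10, split at the median. With gamma shape 1 the crude odds ratio was about 1.08 and 1.31 in the two cases. Shapes from 0.5 to 2 widened the range to 1.05 to 1.47, and shapes from 0.3 to 5 to about 1.02 to 1.8. Within readiness strata it was about 1.0.

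**Step 6. Bias against precision.** Expected abstainers: 112 × 0.071 = 7.95, about 8. With 4 of 56 in each half of a median split, SE(log OR) = √(1/4 + 1/52 + 1/4 + 1/52) = 0.73. The 95% interval runs a factor of exp(1.96 × 0.73) = 4.2 either way. A bias of ln(1.31) = 0.27 is 0.27 / 0.73 = 0.37 SE. The false-positive rates in Step 3 belong to overall abstinence between 0.19 × 0.30 + 0.81 × 0.15 = 18% and 0.5 × 0.45 + 0.5 × 0.15 = 30%. They should not be carried over to a trial with 8 abstainers.

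**The case against.** The strongest reply is that item (3) is framed as a comparison between arms. If readiness confounds equally in both, the difference in slopes is unbiased, and stratification makes equal confounding more plausible. This stands, and it limits the point to the within-arm associations. Stratification does not guarantee equality, though: readiness could relate to commenting differently under tobacco-only and tobacco-plus-alcohol content.

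A reader might infer that the documents show Ready participants commenting more, so that a spurious effect will occur. They do not. The cited result, "Users in the maintenance stage of smoking cessation were more active", compares maintenance with early action, the last two stages of change, on another cessation forum. It does not compare Ready with Not Ready smokers in these groups. It is indirect support, and the most that can be said is that confounding can occur.

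A reader might also infer that later interventions would be misdirected. That goes too far for an exploratory aim in a pilot whose N was not based on hypothesis testing. With about 8 abstainers the random error is larger than the bias in Step 6.

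Finally, adjustment is neither free nor complete. Arm, engagement, their interaction, readiness and smoking pattern make five terms on about 8 events, with a risk of separation. The return to 1.0 in the simulations holds because readiness was built in as the only confounder. These objections stand, and they shape the fix. None of them makes arm imbalance the right way to choose covariates here.

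**Conclusion.** The point holds as a minor one about model specification. The covariate rule in item (3) screens on the wrong criterion, and the stratified design makes readiness and smoking pattern the variables it is least likely to select. Nothing elsewhere in the plan corrects this.

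The consequence is possible bias in the association of comments with abstinence and with heavy drinking inside each arm. For abstinence, with no true effect, the illustrative size is an odds ratio of roughly 1.05 to 1.4. It would be smaller if either link with readiness is weak, and larger if comment counts are less dispersed than assumed (up to about 1.8 in Step 5). These figures rest on assumed links of readiness with commenting and quitting, which the documents do not quantify. No size was worked out for the heavy-drinking model.

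The documents support neither a claim that the bias will occur nor a claim that the between-arm contrast is biased as it stands.

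**What to change.** In item (3), replace the arm-difference rule with covariates fixed in advance:

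- Abstinence model: baseline readiness to quit tobacco and daily/non-daily smoking.
- Heavy-drinking model: baseline readiness to change alcohol use (state which of the two planned measures is used), the two stratification factors, and baseline heavy episodic drinking days.

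Fit the abstinence model by Firth's penalised logistic regression and add no further covariates. State that both sets of results are associational. Comments and outcome build up over the same 3 months, so a participant may comment because they have quit, and baseline adjustment does not remove that.

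The cost is a few sentences. Readiness and smoking pattern are already recorded for stratification, and item (1) already treats alcohol readiness as a baseline characteristic. Confirm that the 30-day drinking count is taken at baseline. The statistical cost is two extra terms in a model with very few events. Penalisation handles separation but does not restore precision, so intervals for the abstinence association will stay wide. Fixing the list in advance also removes a data-dependent choice of covariates.
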